## STUDY PROTOCOL

Study staff will approach pregnant individuals for enrollment who are attending a prenatal appointment between 13-25 weeks gestation. Potential participants who would like time to think over their enrollment decision will be offered a consent form or handout to take home and review, and can contact the study coordinator later if interested. Confirmed eligible participants providing written informed consent will be randomized via computer-generated simple randomization to the experimental or control intervention group (MILK intervention or Text4Baby, respectively). For patients not recruited at the primary enrollment site at MWH (e.g., website; study flyer), arrangements will be made to meet to explain the study, obtain informed consent, randomize to a group, and collect baseline data.

At enrollment, study staff will collect baseline data including demographic, obstetric and breastfeeding history, anxiety, breastfeeding self-efficacy, breastfeeding attitude, breastfeeding intentionality, breastfeeding knowledge, and breastfeeding support via oral administration of paper-based or electronic questionnaire on a study iPad. Data will be inputted into and managed in REDCap (secure, password protected and backed up data management system through University of Pittsburgh). We will also collect contact information for follow-up data collection (email, telephone numbers) and, for participants in the experimental intervention (MILK) group, we will provide written and oral instructions regarding text message frequency and how to stop or reduce volume of text messages (or withdrawal from study). We will provide participants in the control intervention (Text4Baby) instructions about how to sign up for the freely available Text4Baby services. The baseline visit is expected to last an hour or less and will occur either in the prenatal exam room or private MWH space.

Participants in both groups will begin receiving automated prenatal and postpartum texts containing breastfeeding education and support at 25 weeks, and will continue to receive, on average, 3-5 texts weekly through eight weeks postpartum (some MILK texts have multiple parts and are more frequent, particularly in the first week post-birth). Participants in the control group (Text4Baby) will receive more general texts about breastfeeding and infant care, while participants receiving the MILK intervention will receive messages that focus specifically on establishing breastfeeding confidence and behaviors to prevent perceived insufficient milk (PIM). Participants in the MILK group will not be excluded from study participation if they sign up to receive Text4Baby messages. Rather, we will assess receipt of Text4Baby messages in both groups at each data collection point. At enrollment, both groups will be provided contact information for local lactation support resources for as-needed individualized breastfeeding support.

**Experimental Intervention (MILK):** The experimental MILK intervention is based on the Breastfeeding Self-Efficacy (Social Cognitive Theory) conceptual model that theorizes self-efficacy as a primary driving force of breastfeeding behavior, and PIM as a consequence of impaired breastfeeding self-efficacy. Prenatal texts encompass general aspects of breastfeeding management; positive reinforcement regarding the decision to breastfeed; information about breastfeeding benefits and current breastfeeding recommendations; and anticipatory guidance regarding how breastfeeding “looks” and works (e.g., interactive website links featuring real moms breastfeeding). While participants will have the option to text the study immediately about delivery of their infant(s), and thus drive the conversion to postpartum-

oriented messages, we will monitor MWH participant hospital delivery records roughly daily for this purpose. In the postpartum period, texts will continue at roughly the same frequency, but anticipatory guidance about breastfeeding will be modified based on infant's gestational age (e.g., milk expression for preterm infant) and time since delivery (e.g., feeding expectations at 24 hours versus 1 week). Texts include guidance related to milk volume, infant breastfeeding behavior, and technical aspects (positioning/latch); referrals to local and online support groups; and encouragement. Participants will be able to text a key phrase to reduce message frequency or stop messages altogether. We have also added automated personalization and interactivity, such that participants and their infants will be addressed by name and some texts attempt to engage participants by requesting responses, with follow-up texts or web links addressing concerns in greater detail. To provide the assistance needed while still maximizing sustainability, participants experiencing complex breastfeeding issues will have the option to request individualized support from study lactation consultants via the text message system (texting a keyword, which will then be followed by study lactation consultant following up with participant via the participant's preferred communication medium). We will keep a log of issues addressed in individual consults to inform future modifications to the MILK intervention. In addition, consults will be audio-recorded (if by telephone) or saved as electronic files (if via text or email) in order to later review content in detail for future interviews and assure adherence to study protocol.

**Control Intervention (Text4Baby):** The national, free, automated text message system, "Text4Baby," was developed by the National Healthy Moms, Healthy Babies Coalition in collaboration with the Centers for Disease Control and Prevention. The system—rigorously developed through expert review, research, and input from pregnant and postpartum women, is designed to provide perinatal health support and information to women from pregnancy up to one year after delivery. Messages are updated annually and address various aspects of maternal and infant prenatal and postpartum care, including safe sleep, infant developmental milestones, and breastfeeding. Conversion to postpartum messages is automatic, based on gestational data provided by users. Similar to participants in the MILK intervention, participants in the control group will also receive contact information for study lactation consultants to converse by telephone, email, etc. Participants will receive a total of 3-5 text messages per week during pregnancy and postpartum from a database containing more than 250 messages. There are seven total prenatal breastfeeding messages, which begin in week 25. There are 8 total postpartum breastfeeding-specific messages commencing at 2 weeks postpartum, and continuing in weeks 7, 8, 13, 18, 24, 28, and 50. Participants may continue to receive Text4Baby messages after 8 weeks, but study data collection will end at that point. Participants can text a "STOP" reply to discontinue these messages. Research personnel will not receive any data from Text4Baby. Rather, participants will self-report their use/whether they are receiving texts from this system as part of the questionnaire data. Participants assigned to Text4Baby will be provided instructions regarding how to register with the system (texting BABY to [name] or signing up on website); when signing up, participants will be prompted to enter their phone number, zip code, an email, their age, and the due date of the baby. Text4Baby does not sell information to any third parties but may share de-identified data with Health Insurance Plans, Government Health Departments, and academic research organizations. Users have the right to request deletion of their personal identifiable information stored by Text4Baby via email. Text4Baby web servers automatically collect non-personal information such as the domain name of the Internet access provider, the Internet protocol address used to

connect the computer to the Internet, the average time spent on the website, pages viewed, information searched for, and access times. Participants can disable cookies to restrict this monitoring.

After enrollment, we will collect data from participants remotely at 34-36 weeks of pregnancy, and at 1, 2, 5, and 8 weeks postpartum and 6 months postpartum. We collect birth hospitalization and feeding data via the birth electronic medical record after birth. At 34-36 weeks of pregnancy, we will collect questionnaire data regarding breastfeeding self-efficacy, breastfeeding intentions, and maternal employment (covariate impacting breastfeeding) via an electronic REDCap survey link sent to participants via email. At 1, 2, 5, and 8 weeks postpartum, we will collect data including breastfeeding self-efficacy, anxiety, depression, breastfeeding knowledge, perceived milk supply, infant feeding status, feeding activities, breastfeeding support, and receipt of Text4Baby texts via REDCap survey (emailed link to participants). All participants will be assigned a number (chronological based on enrollment order), and this will be used on all data collection instruments (including emailed surveys), rather than participant's real name. Research staff or the PI will review survey responses within two days of completion to assess missing/non-sensical data. Research staff will attempt to contact participants by phone to resolve missing or non-sensical data upon identification of the issue. Time for participants to complete remote surveys is estimated at no more than 30 minutes. They may begin a survey and return to it. Participants will have approximately 1 week to complete surveys. A reminder email will be sent at 3 days if no survey is received. We will attempt to call participants up to three times to complete questionnaires over the phone if no electronic survey is completed after the email reminder at 3 days. Note that we will also call participants by phone without emailing a survey first if they prefer a phone call. The timepoints chosen for data collection were based on the higher prevalence of perception of insufficient milk and early breastfeeding cessation in the first 1-2 months postpartum.

At the conclusion of the main study (8 weeks), we will conduct individual telephone interviews with approximately 25% of participants in the Text4Baby control group (to be selected purposively based on mutual availability of research and participant and variability in participant characteristics known to impact breastfeeding, e.g., age, race). This individual interview will be offered to all MILK (experimental group) participants to assess intervention use, burdens and challenges, and suggested modifications. Interviews are expected to last 30-60 minutes, and will be audio-recorded and transcribed verbatim. A list of MILK text messages will be sent to participants in the intervention group ahead of the interview for reference. All interviews will be conducted and analyzed by the PI or research assistant(s)/coordinator who have or will have training in qualitative interviewing.

Breastfeeding continuation and exclusivity (i.e., supplementation behaviors) will be assessed via a follow-up telephone call at 6 months postpartum. We will place up to 3 follow-up calls to make contact with study participants.

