## STATISTICAL ANALYSIS PLAN

Data will first be screened for anomalies (e.g., outliers, non-normality, missing data, imbalances between groups). If anomalies are encountered, appropriate remedial strategies will be applied

(e.g., data transformation, imputation, statistical adjustment of covariates, etc.) prior to primary analyses. We will analyze efficacy outcomes using an intention-to-treat approach, but also conduct sensitivity analyses and perform comparisons based on protocol deviations (e.g., comparisons between participants who do and do not receive all texts, participants in the intervention group who receive Text4Baby). Between group (each time point) and group  $\times$  time differences will be examined graphically and via generalized mixed-effects modeling for all outcome variables of interest. For our main outcome of breastfeeding exclusivity at 8 weeks and other categorical outcome variables (e.g., any breastfeeding at each follow-up), we will use chi-square test statistics and logistic regression (if statistical adjustment is needed) to determine between-group differences. For continuous-type outcome variables (e.g., perceived milk supply/confidence scores), we will assess between-group differences at postpartum follow-ups via analysis of variance procedures (e.g., ANCOVA, ANOVA) or analogous nonparametric methods.

We will descriptively analyze study participation, attrition, and intervention use (e.g., proportions with 95% CIs). We will also explore possible predictors of participation (yes, no) and intervention use (yes, no) with group comparative statistics (e.g., independent sample t-tests and chi-square test statistics or binary logistic regression for continuous and categorical variables, respectively). The PI will code interview data for major themes using Atlas TI. The interview script will be modified on a continual basis to include new perspectives broached by participants.

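### The main 8-week comparison pairs simple randomization with an unadjusted chi-square test, which is valid but gives up a little precision that a pre-specified adjustment for breastfeeding history would recover

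*Combined protocol and SAP*

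**What the plan says.** The STUDY PROTOCOL section states that consenting participants "will be randomized via computer-generated simple randomization to the experimental or control intervention group". It mentions no blocking, stratification or minimization, and no allocation ratio.

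The same section says that staff collect "baseline data including demographic, obstetric and breastfeeding history, anxiety, breastfeeding self-efficacy, breastfeeding attitude, breastfeeding intentionality, breastfeeding knowledge, and breastfeeding support". None of these is named as a stratification factor or a model covariate. For recruits who come by website or flyer, the steps are listed as consent, then randomization, then baseline data.

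The STATISTICAL ANALYSIS PLAN section begins with a screen: "Data will first be screened for anomalies (e.g., outliers, non-normality, missing data, imbalances between groups". If anomalies are found, remedies that include covariate adjustment may be applied before the primary analyses. For 8-week exclusivity and other categorical outcomes, "we will use chi-square test statistics and logistic regression (if statistical adjustment is needed) to determine between-group differences". No covariates are listed and no trigger for adjustment is given.

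**The concern.** Under simple randomization, the balance of any baseline predictor between arms is left to chance. An unadjusted chi-square then carries that chance imbalance as noise. Design or analysis can remove it, and the plan fixes neither in advance: allocation uses no predictor, and adjustment is conditional on what the screen shows.

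At stake is some precision and power on the main outcome, plus the clarity of the primary analysis. With no covariate list and no trigger, whether and how to adjust is settled after the groups have been compared.

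**Working it through.** The plan gives no sample size, power, alpha, control rate or effect size, so there is no figure of its own to reproduce. Everything below is under stated assumptions.

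**Assumptions.** 1:1 allocation; two-sided 5% test; N = participants with an 8-week outcome, from 60 to 400; one binary predictor with 50% prevalence; exclusivity 25% and 55% in its two levels (30-point gap, 40% overall).

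**1. Arm sizes.** The SE inflation for a split with fraction f in one arm is 1/√(4f(1−f)).
- 55:45: 1/√(4 × 0.55 × 0.45) = 1.005, or 0.5%.
- 60:40: 1/√(4 × 0.60 × 0.40) = 1.021, or 2.1%.

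The chance of 60:40 or worse is 15.5%, 5.7%, 0.6% and 0.01% at N = 60, 100, 200 and 400. Averaged over all splits, the inflation is 0.87% at N = 60 and 0.25% at N = 200. The mean power loss for 40% v 55% is at most 0.3 points.

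**2. Share of variance due to the predictor.**
- Total: 0.40 × 0.60 = 0.24.
- Within levels: 0.5 × 0.25 × 0.75 + 0.5 × 0.55 × 0.45 = 0.2175.
- Between levels: 0.30² × 0.25 = 0.0225, which is 9.4% of 0.24.
- SE ratio: √(0.24/0.2175) = 1.05, so chance imbalance adds about 5%.

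This ratio does not depend on N. At N = 200 the SE is √(4 × 0.24/200) = 6.9 points with the imbalance and √(4 × 0.2175/200) = 6.6 without it. The 95% half-width goes from 13.6 to 12.9 points.

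**3. Range over the assumed gap.** With a 40-point gap (20% and 60%), the within-level variance is 0.20 and the SE ratio is √(0.24/0.20) = 1.095, or about 10%. With a 10-point gap, the between-level part is 0.10² × 0.25 = 0.0025 and the ratio is √(0.24/0.2375) = 1.005, or about 0.5%.

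**4. Chance of visible imbalance, and power.** The gap in the predictor comes from 200,000 simulated draws. Power for a 15-point effect comes from 40,000 simulated trials per cell. The adjusted test is the Cochran-Mantel-Haenszel (CMH) test.

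| N | Gap of 10 points or more | Shift in risk difference (SD, points) | Simple + chi-square | Simple + CMH | Stratified + chi-square | Stratified + CMH |
|---|---|---|---|---|---|---|
| 60 | 46% | 3.9 | 21.7% | 22.2% | 20.8% | 22.6% |
| 100 | 33% | 3.0 | 33.0% | 34.4% | 33.7% | 35.0% |
| 200 | 16% | 2.1 | 57.1% | 60.2% | 59.3% | 60.8% |
| 400 | 5% | 1.5 | 85.4% | 88.4% | 86.9% | 88.7% |

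At N = 200, adjustment alone gains 60.2 − 57.1 = 3.1 points. Stratified allocation on top adds 60.8 − 60.2 = 0.6. The simulation error of one cell is about √(0.6 × 0.4/40,000) = 0.24 points, so 0.6 is barely distinguishable from noise.

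**5. Validity.** With no true effect, the chi-square under simple randomization rejects in 4.9–5.2% of trials. Under stratified allocation, an unadjusted chi-square rejects in 3.7–4.4%. It becomes conservative, so strata that are left out of the analysis waste part of their benefit.

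**The case against.** The strongest reply is that simple randomization is a legitimate choice. It is fully unpredictable, which matters because staff who enroll participants also give arm-specific instructions, and the documents describe no blinding. Chance imbalance is already inside the sampling error that the test and its interval reflect: at N = 200 a shift with SD 2.1 points sits inside a half-width of 13.6. The SAP also permits adjustment. All of this stands. It moves the main remedy from the allocation to the analysis, where permission to adjust falls short of a commitment.

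A reader might infer more than the documents support:
- *That the comparison is biased or its type I error inflated.* The rejection rate stays near 5% when the chi-square is used throughout. The rule of choosing the analysis after screening was not simulated, so no claim is made about it.
- *That unequal arms matter.* They cost 0.5% of the SE at 55:45.
- *That the SAP expects to need repairs.* Its wording is conditional.
- *That this is a single-center trial.* The text says "For patients not recruited at the primary enrollment site at MWH (e.g., website; study flyer", which names a primary site and allows other routes.
- *That breastfeeding history is the strongest predictor.* The documents rank none. They call self-efficacy a primary driver, and refer to "variability in participant characteristics known to impact breastfeeding, e.g., age, race" only when choosing interviewees.

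**Conclusion.** The point holds as a modest loss of efficiency in a valid design. For one predictor of the assumed strength, the SE of the main risk difference is about 5% larger than it need be. In sample-size terms that is 0.24/0.2175 = 1.10, or about 10% more participants for the same precision. Power at an assumed N of 200 is about 57% with the planned chi-square and about 60% with fixed adjustment. The 57% describes the plan's default branch; where screening did trigger adjustment, some of the difference could be recovered.

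The size depends on the gap in exclusivity across the predictor: about 0.5% of the SE at 10 points and about 10% at 40. The proportional loss does not depend on N. What grows as N falls is the chance of a visible imbalance, from 16% at N = 200 to 33% at N = 100 and 46% at N = 60. That is why stratified allocation has most to offer at N of about 100 or less, although the simulated power gain from it is small at every N.

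**What to change.** **Main change (STATISTICAL ANALYSIS PLAN).** Make the primary 8-week exclusivity analysis a logistic regression, or a CMH test, that always adjusts for breastfeeding history (none/any), whatever imbalance is observed. Keep the unadjusted chi-square as a secondary result. If logistic regression is used, name the effect measure, since the adjusted odds ratio is not the same quantity as the crude one. Settle this before outcomes are seen by arm. If the enrolled population turns out to have little variation in history, fix another listed baseline item instead.

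**Supporting change (STUDY PROTOCOL).** Record breastfeeding history before allocation for all recruits. The sequence listed for off-site recruits puts randomization ahead of baseline data.

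**Optional change (STUDY PROTOCOL), most useful if N is about 100 or less.** Stratify allocation on the same factor, using permuted blocks of randomly varied, undisclosed size with the list concealed until consent is recorded. Keep the stratifier in the model. If enrollment is under way, apply this to the remaining allocations.

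**Cost.** The main change costs an SAP revision and one question moved ahead of allocation. The optional change needs a new allocation list and brings slight predictability at block ends, because staff learn assignments when they give arm-specific instructions and no blinding is described. Varied block sizes limit this but do not remove it.

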## STATISTICAL ANALYSIS PLAN

Data will first be screened for anomalies (e.g., outliers, non-normality, missing data, imbalances between groups). If anomalies are encountered, appropriate remedial strategies will be applied

(e.g., data transformation, imputation, statistical adjustment of covariates, etc.) prior to primary analyses. We will analyze efficacy outcomes using an intention-to-treat approach, but also conduct sensitivity analyses and perform comparisons based on protocol deviations (e.g., comparisons between participants who do and do not receive all texts, participants in the intervention group who receive Text4Baby). Between group (each time point) and group  $\times$  time differences will be examined graphically and via generalized mixed-effects modeling for all outcome variables of interest. For our main outcome of breastfeeding exclusivity at 8 weeks and other categorical outcome variables (e.g., any breastfeeding at each follow-up), we will use chi-square test statistics and logistic regression (if statistical adjustment is needed) to determine between-group differences. For continuous-type outcome variables (e.g., perceived milk supply/confidence scores), we will assess between-group differences at postpartum follow-ups via analysis of variance procedures (e.g., ANCOVA, ANOVA) or analogous nonparametric methods.

We will descriptively analyze study participation, attrition, and intervention use (e.g., proportions with 95% CIs). We will also explore possible predictors of participation (yes, no) and intervention use (yes, no) with group comparative statistics (e.g., independent sample t-tests and chi-square test statistics or binary logistic regression for continuous and categorical variables, respectively). The PI will code interview data for major themes using Atlas TI. The interview script will be modified on a continual basis to include new perspectives broached by participants.

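### Whether the main 8-week exclusivity comparison is covariate-adjusted is left to an undefined decision after data screening; one analysis should be fixed in advance

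*Combined protocol and SAP*

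**What the plan says.** The SAP begins with a screen for anomalies. Its examples include "missing data, imbalances between groups", and its example remedies include "statistical adjustment of covariates, etc.) prior to primary analyses". For the main outcome, exclusivity at 8 weeks, and for other categorical outcomes it then states: "we will use chi-square test statistics and logistic regression (if statistical adjustment is needed) to determine between-group differences". It gives no definition of need, no imbalance threshold, no covariate list and no fixed adjusted model. It also plans "generalized mixed-effects modeling for all outcome variables of interest", again without naming covariates.

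Under Study Protocol, allocation is by "computer-generated simple randomization". Enrollment collects "baseline data including demographic, obstetric and breastfeeding history, anxiety, breastfeeding self-efficacy, breastfeeding attitude, breastfeeding intentionality, breastfeeding knowledge, and breastfeeding support". For people recruited away from the primary site, the steps are listed as "obtain informed consent, randomize to a group, and collect baseline data". The survey at 34-36 weeks repeats self-efficacy and intentions and adds maternal employment, the only variable that the documents label a covariate.

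The documents state no sample size, alpha, power, exclusivity rate or target difference.

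**The concern.** Two things are wrong with leaving adjustment to a judgment made on the data.

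First, the reason for adjusting is the wrong one. With simple randomization any baseline difference arises by chance, so a screen for imbalance tests something already known. Adjustment earns its place when a covariate predicts the outcome, whatever its observed balance. The protocol's own conceptual model treats self-efficacy as a main driver of breastfeeding behavior, so the trial team expects at least one enrollment measure to be predictive. The default test leaves it out.

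Second, the choice stays open. Because need is undefined, two analyses of the main outcome are available after the data have been seen, and nothing written says which one counts.

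At stake are some precision, if the covariates predict and the trial is not small, and protection against a result-driven choice between two p-values.

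**Working it through.** The plan has no figure to reproduce. Every rate, N and predictor strength below is an assumption.

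**1. How often would an imbalance rule fire?** With k independent variables each tested at p<0.05, the chance of at least one flag is 1 - 0.95^k.

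- k = 3: 1 - 0.95^3 = 14.3%.
- k = 9 (the enrollment list contains nine domains): 1 - 0.95^9 = 37.0%. With correlation 0.4, simulation gave 30%.
- Standardized difference above 0.2, equal arms: the SE of the difference is 2/√N, or 0.20 at N=100. Then P(|Z|>1) = 0.317 per variable, and three variables give 1 - 0.683^3 = 68%. At N=200 the SE is 0.141, P(|Z|>1.41) = 0.157, and 1 - 0.843^3 = 40%.

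The firing rate depends wholly on two things the SAP does not state: the number of variables screened and the threshold.

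**2. Type I error.** Simulation B: simple randomization, three independent normal covariates, 30% vs 30%, 4,000 trials per cell, N = 40 to 200.

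- Mechanical rule (adjust only for covariates flagged at about p<0.05): 3.8-5.8%.
- Reporting whichever of chi-square and adjusted model is significant: 5.8-8.7%.

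**3. What a fixed model gains.** Simulation A: 35% vs 50%, 1:1, 20,000 trials per cell. There are three covariates, two normal and one binary, with latent correlation 0.4. The standardized risk difference comes from logistic regression on arm plus the three covariates, with a leverage-corrected robust SE and a t reference on N-5 df. It is compared with the chi-square at N = 60/100/200/300. A variance ratio (adjusted/unadjusted) below 1 is a gain.

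| Log-OR per SD | AUC | Variance ratio | Power change (points) |
|---|---|---|---|
| 0, 0, 0 | 0.50 | 1.06/1.03/1.01/1.01 | -2.3/-2.6/-1.1/-0.9 |
| 0.2 each | 0.62 | 1.00/0.99/0.97/0.96 | -1.8/-1.0/+0.6/+1.1 |
| 0.7, 0, 0 | 0.68 | 0.96/0.93/0.91/0.91 | -0.9/+0.2/+2.9/+3.0 |
| 0.4 each | 0.73 | 0.90/0.88/0.86/0.87 | +0.3/+2.2/+5.6/+5.6 |

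Type I error of the fixed model was 4.5-5.2% and CI coverage 94.9-95.5%. The small-sample correction matters: at N=60 an uncorrected robust SE gave 6.8-7.4% type I error, and a degrees-of-freedom correction alone 5.6-6.0%. A repeat of the first and last rows with 6,000 trials per cell gave, at N=200, -1.1 and +5.3 points.

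Simulation B under 30% vs 45%, using the Wald test for arm (a slightly more favorable test), chi-square then fixed model:

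| R² | N=100 | N=200 |
|---|---|---|
| 0 | 34.0% to 33.7% | 59.1% to 58.5% |
| 0.09 | 33.3% to 35.3% | 58.7% to 62.7% |
| 0.21 | 34.5% to 40.3% | 60.2% to 69.6% |
| 0.34 | 35.1% to 46.6% | 61.4% to 77.2% |

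The two sets agree in pattern: a small loss when nothing predicts, and a gain that grows with predictor strength. At N=40 in simulation B the change was between -1.2 and +0.2 points at every strength.

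**4. Timing of candidate covariates.** Texts start at 25 weeks. The later prenatal survey falls 34 - 25 = 9 to 36 - 25 = 11 weeks after that, so its measures come after allocation and after exposure.

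**The case against.** The strongest reply is that this is an efficiency preference. The chi-square is a valid test, and without N, rates or predictor strength the benefit cannot be sized or even signed: in simulation A it runs from -2.6 to +5.6 points. That stands, and it keeps this a recommended improvement rather than a correction. It does not answer the second half of the point, because an undefined choice between two analyses is worth closing at any sample size.

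A reader might infer more than the documents support in five places.

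- *Imbalance is the only trigger.* This is the natural reading, but the SAP never says so.
- *The rule would rarely fire, so the reported interval and power would hardly change.* This holds for a screen of three variables at p<0.05, which the SAP does not specify. Step 1 gives 14% to 68% under equally plausible screens.
- *The rule inflates type I error.* A mechanically applied one does not. The 6-9% requires picking by result, which the wording permits but does not plan.
- *The mixed-effects model competes as the main test.* The SAP assigns the main outcome specifically to chi-square or logistic regression.
- *The plan will adjust for post-allocation measures.* Labeling employment a covariate does not place it, or the 34-36-week scores, in the main model. The timing is a guard to build into the fix, not an error found in the plan.

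**Conclusion.** The point holds as one of pre-specification and efficiency, with medium confidence. The SAP lets a post-screening judgment decide whether the main outcome is adjusted. It does not define that judgment, and the reason it suggests, imbalance, is the wrong one under simple randomization.

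The size is conditional. With N of 200 or more and the assumed rates, a fixed model changed power by about -1 point with useless covariates, up to about +6 in simulation A and +9.4 in simulation B at R² = 0.21. An R² of 0.34 would give +15.8, but nothing in the documents supports predictors that strong. At about N=100 or fewer the gain is not dependable: at N=100, simulation A ranged from -2.6 to +2.2 points, and only the stronger predictors in simulation B did better.

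**What to change.** Delete the imbalance trigger and the parenthesis that makes logistic regression conditional. Before any data are screened, write down one primary analysis of 8-week exclusivity.

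- **Preferred, if planned N is well above 100:** logistic regression on arm plus two or three enrollment measures already collected (for example self-efficacy, intentionality and breastfeeding history), used whatever the balance. Report a standardized risk difference, with its 95% CI and p-value from that same estimate, using a leverage-corrected robust SE or a bootstrap. Naming the effect measure matters, because the adjusted odds ratio is a different, conditional quantity.
- **If planned N is about 100 or fewer:** the sponsor may instead fix the chi-square as the only primary analysis.

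In either case label the other test, and the mixed-effects model for this outcome, as supportive. Adjust only for measures completed before allocation is revealed: place the questionnaire before randomization for off-site recruits, and state the same order at the primary site. Do not adjust for 34-36-week measures, including employment as collected then.

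The cost is SAP wording and one line in the enrollment procedure, with no added participants or measures. The downside is real but small: if the chosen covariates do not predict exclusivity, variance rises 1-6% and power falls about 1-3 points.
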